
Purpose and Objectives

The overall objective of this study is to evaluate the effectiveness of a mindfulness-based intervention to prevent weight regain in weight-reduced adults.

A secondary objective is to perform preliminary efficacy testing comparing the impact of MORE vs standard weight loss maintenance advice (CON) on weight loss maintenance and eating-related behaviors (disinhibition, hedonic hunger, food cravings, and ad libitum energy intake).

To meet these objectives, we propose the following aims:

Specific Aim 1: Determine the effect of MORE on weight loss maintenance.

Hypothesis: MORE will result in less weight regain compared to CON after the 8-week intervention, and benefits will be sustained in a 6-month follow-up.

Specific Aim 2: Determine the effect of MORE on reward-related behavioral processes (e.g., food cravings) and ad libitum energy intake.

Hypothesis: MORE group will demonstrate changes in eating behaviors and energy intake associated with preventing weight regain compared to CON immediately after MORE and after 6-months of follow-up.

Study Population

Age of Participants: 18-65

Sample Size:

At Utah:

All Centers: 100

Inclusion Criteria:

We will enroll the following three subgroups (ages 18-65 years):

- Lifestyle weight loss: weight loss of 7% body mass via intentional weight loss within past 6 months; BMI $>25 \text{ kg/m}^2$ prior to intentional weight loss.
- Medical weight loss patients: patients of the bariatric weight loss clinic, weight loss of 7% body mass via intentional weight loss within past 6 months; BMI $>25 \text{ kg/m}^2$ prior to intentional weight loss; stable for 3 months on medications.
- Bariatric Surgery patients: 12-20 months post-operation.

Exclusion Criteria:

Exclusion Criteria: uncontrolled cardiovascular, metabolic, renal, or pulmonary disease; cancer treatment in past 5 years; untreated thyroid disease or other medical condition affecting weight or energy metabolism; severe food allergies; women who are pregnant, lactating, or planning pregnancy during participation in the trial; active psychiatric issues. Scheduled bariatric surgery within the next 6 months. No access to WiFi at residence. No access to a smart device as a personal device (with access to applications). Complete hearing loss.

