OPTIONAL POST-INTERVENTION TESTING AT 1 YEAR: 6 months after the post-intervention testing time point participants will be contacted and asked to complete follow-up questionnaires. These questionnaires are designed to assess participants' perceptions of the intervention and if they achieved their weight-loss maintenance goals.

STOPPING PROCEDURES and ADVERSE EVENTS: Participants will be encouraged to report any adverse events that they believe may have been a result of the study.

Procedures performed for research purposes only:

Statistical Methods, Data Analysis and Interpretation

The statistical analysis plan presented below was developed in collaboration with [name] of the SDBC.

Aim 1 will focus on the efficacy of the intervention (MORE vs. CON) on the primary outcome of body mass and body composition at week 8 and week 24. We will first provide descriptive summaries of each variable measured at week 0 (baseline), week 8 and 24, as well as by intervention group. Linear mixed models (LMM) will then be used to relate weekly assessments of body mass from week 0 to week 24 to the intervention, controlling for covariates likely to be associated with the outcome. Specifically, this will include baseline body mass and composition, and other demographic covariates including (but not be limited to) age, sex, race and socioeconomic status. Different slopes for time trend and intervention-time interaction term will be assumed for the intervention period (week 0-8) and follow-up period (week 8-24). Random intercepts will be used to account for correlations on the participant level. An advantage of this approach is treatment effect estimates remain consistent and approximately unbiased if missing data follow a missing-at-random pattern (MAR; data values are independent of missingness mechanism conditional on the observed data), the most general data-centric missing data assumption. Secondary analyses will fit separate LMM models to assess changes in fat mass and lean mass measured at week 0, 8 and 24. Similarly, LMM will be fitted for each of the eating behaviors and energy intake outcome collected for **Aim 2** (detailed above), where skewed outcomes may be transformed to approximate normality. Bonferroni correction will be performed to adjust for multiple comparisons.

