Sample size, and power consideration: For a total of 100 participants randomized 1:1 to each study arm, we conservatively anticipate 20% attrition. This leaves us with complete data on n=80 participants total (n=40 per group). This provides $\geq 80\%$ power for detecting differences in body mass (or other outcomes assessed in Aim 1 and 2) by at least 0.89 standard deviations. We expect power will be greater for our primary analysis models when adjusting for covariates associated with outcomes. Although we will have limited statistical power for the current analysis this trial will generate the effect size necessary to power a future trial, while allowing us to collect outcome measures on a practical amount of participants within the 2-year award period.

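### Body composition is named primary and then analysed as secondary, and no primary contrast, alpha or Bonferroni family is defined, so the threshold for the main weight test is left open

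*Combined protocol and SAP*

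**What the plan says.** All references are to the combined protocol and SAP.

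- **Primary outcome.** Under Statistical Methods, Data Analysis and Interpretation, Aim 1 addresses the "primary outcome of body mass and body composition at week 8 and week 24".
- **Main model.** A linear mixed model will "relate weekly assessments of body mass from week 0 to week 24 to the intervention". It has separate time slopes and separate intervention-by-time terms for weeks 0 to 8 and weeks 8 to 24. Neither term, nor any combination of them, is called the primary test.
- **Body composition.** The same paragraph continues: "Secondary analyses will fit separate LMM models to assess changes in fat mass and lean mass measured at week 0, 8 and 24". These are the only body-composition models in the plan.
- **Multiplicity.** Straight after the sentence on the Aim 2 outcomes comes the whole rule: "Bonferroni correction will be performed to adjust for multiple comparisons". The documents state no alpha, sidedness, family or count.
- **Sample size.** The paragraph on sample size and power takes 100 participants, 1:1, with 20% attrition, leaving 40 per group. It claims at least 80% power for a difference of at least 0.89 SD. That one figure serves body mass and every other Aim 1 and Aim 2 outcome.
- **Objectives.** Under Purpose and Objectives, the overall objective and Specific Aim 1 both concern preventing weight regain. Weight loss maintenance appears again, beside the eating behaviours, in the sentence that begins "A secondary objective is to perform preliminary efficacy testing".

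**The concern.** A reader who wants to know which result decides the trial cannot find out. Body composition has two roles in one paragraph, two time points are both primary, and the body-mass model yields two period-specific treatment terms. The Bonferroni sentence might apply to body mass, to body composition, to the Aim 2 outcomes or to all of them.

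The threshold for the main weight claim therefore remains to be chosen, possibly after results are known. A lenient choice leaves the false-positive rate of the headline claim uncontrolled. A severe one gives up much of the power for the weight question to outcomes that the plan itself treats as secondary. The second risk matters here because the sample size paragraph already concedes limited power.

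**Working it through.** **Inputs.** From the sample size paragraph: N = 100, 1:1, 20% attrition, power at least 80%, difference 0.89 SD. Assumed, because the documents give none: two-sided test and base alpha 0.05. All figures are for an unadjusted comparison of two means with SD = 1.

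**1. Attrition.** 100 × 0.80 = 80, or 40 per arm. The plan's arithmetic is correct.

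**2. The plan's 0.89 SD.** By the normal approximation the detectable difference is

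d = (z₁₋α/₂ + z₀.₈₀) × √(2/n) = (1.960 + 0.842) × √(2/40) = 0.626 SD.

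The noncentral t version (78 degrees of freedom, noncentrality d√(n/2)) gives 0.634 SD. At 0.89 SD, power is 97.6% (t) or 97.8% (normal). The stated figure is 0.89/0.634 = 1.40 times the value for one test at 0.05, so it is not reproduced. Other conventional settings with 40 per arm do not reach it either (t version):

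- one-sided 0.05, 80% power: 0.561
- two-sided 0.05, 90% power: 0.734
- two-sided 0.05, 95% power: 0.816

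**3. What would give 0.89.** Several unstated inputs fit or nearly fit:

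- Solving the t version for alpha gives 0.0025 = 0.05/20, so 20 Bonferroni tests.
- The normal approximation gives alpha 0.0017, about 29 tests.
- 20 per arm with no correction gives 2.802 × √(2/20) = 0.886 by the normal approximation (0.909 by t).
- A variance inflation of (0.89/0.634)² = 1.97 at 0.05 would also do it.

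**4. What the open threshold is worth.** With 40 per arm, two-sided, alpha = 0.05/k, noncentral t:

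| Tests sharing alpha (k) | A reading that gives k | Alpha per test | Detectable at 80% power | Power at 0.634 SD |
|---|---|---|---|---|
| 1 | body mass, one time point | 0.05 | 0.634 SD | 80% |
| 2 | body mass, two time points | 0.025 | 0.701 SD | 71% |
| 4 | mass and composition, two time points | 0.0125 | 0.762 SD | 61% |
| 6 | mass, fat and lean, two time points | 0.0083 | 0.796 SD | 55% |
| 20 | value that fits 0.89; not in the documents | 0.0025 | 0.890 SD | 39% |

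The role conflict and the two time points alone account for at most k = 6, or 0.796 SD. On the multiplicity explanation, reaching 0.89 would need a family that also takes in Aim 2 outcomes.

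**5. Why the contrast must be named.** Suppose the slopes are per week and join at week 8, with b₁ and b₂ the intervention-by-time coefficients for the two periods. The between-arm difference in change from baseline is 8b₁ at week 8 and 8b₁ + 16b₂ at week 24. A test of b₂ alone asks whether the arms diverge after week 8, which is a different question from whether they differ at week 24. Naming a time point without the contrast still leaves a choice.

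**The case against.** The other side has several fair points.

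- **A reader might infer that the alpha is contradictory.** It is not: no alpha is stated, so it is undefined. The contradiction is in the role of body composition.
- **A reader might infer that 0.89 SD proves that body mass shares alpha with about 20 tests.** One figure for all outcomes is consistent with that, but the number is back-solved and not unique (step 3). The rival of 20 per arm would conflict with the stated 40 per group, and nothing in the plan mentions a variance inflation, although both arms are group-delivered. None of these explanations is documented. The 39% power in the last row of the table is therefore an illustration, not a property of the plan.
- **The power sentence is literally true.** It says at least 80%, and power at 0.89 SD is 97.6% at 0.05, 95.3% at 0.025 and 89.5% at 0.05/6. True, but it then says nothing about what one primary test can detect.
- **A reader might infer that the objectives demote the weight question.** The overall objective and Specific Aim 1 both put weight regain first. The secondary objective repeats it, which is untidy and no more.
- **A reader might infer gross error inflation.** Six independent uncorrected tests would give 1 − 0.95⁶ = 26%. That requires ignoring both the Bonferroni sentence and the one that makes fat and lean mass secondary. The documents do not support it.
- **The figures are not for the planned model.** The adjusted mixed model should do somewhat better, as the sample size paragraph expects. This stands, and 0.63 SD should be read as an unadjusted benchmark.
- **Bonferroni is valid and the trial is preliminary.** Bonferroni controls error once its family is defined, so a fixed sequence is a gain in efficiency rather than a requirement. But the plan states a directional efficacy hypothesis and promises a formal correction, so it still has to say which test and which family.

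**Conclusion.** The point holds as a gap in definition. Body composition is both primary and secondary in one paragraph, no primary contrast or time point is designated, and the Bonferroni rule lacks an alpha, a family and a count.

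Within the readings that the outcome wording allows (1 to 6 tests), the detectable difference runs from 0.63 to 0.80 SD, and power at 0.634 SD runs from 80% down to 55%. Separately, 0.89 SD is not the 80% detectable difference for one primary test at two-sided 0.05, and its origin cannot be established from the documents.

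These sizes rest on an assumed two-sided 0.05, 40 analysed per arm and an unadjusted two-group comparison. The gap in definition depends on none of these. It should be corrected, but it does not invalidate the design.

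**What to change.** Amend the statistical section, before anyone examines outcome data by arm, as follows.

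1. Declare body mass the single primary outcome. Name one model contrast at one time point, tested at two-sided 0.05, and write it in terms of the model coefficients.
2. Test body mass at the other time point in fixed sequence, at the same level, only if the first test succeeds. Week 8 followed by the follow-up visit matches the order of the Aim 1 hypothesis, but the choice is the sponsor's.
3. State that fat mass and lean mass are secondary, and remove body composition from the primary-outcome sentence.
4. Confine Bonferroni, or the more powerful Holm procedure, to the secondary and Aim 2 family, and list its members.
5. Restate the detectable difference with its alpha and sidedness (about 0.63 SD for the primary test, unadjusted), or state the alpha and number of tests behind 0.89 SD.
6. Tidy the secondary objective so that it does not list weight loss maintenance a second time.

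The cost is wording only, with no extra participants or visits. There are two small downsides: body composition can no longer support a primary claim, and the second time point can be claimed only if the first is met.

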- **Randomization:** Following enrollment and completion of baseline testing a randomization assignment will be generated by computer and block randomization will be performed within strata defined by sex. Participants will be randomized 1:1 to MORE or CON

INTERVENTION:

Group-Based Interventions

- **MORE:** Participants randomized to MORE will complete the previously developed 8-week, MORE program (E. Garland, 2013). MORE is delivered in a group format, consisting of 8 weekly HIPPA compliant virtual zoom 2-hour sessions. The MORE curriculum will be adapted for this intervention to address food intake behaviors and will provide training in mindfulness techniques to increase awareness of, and self-control over, cravings; reappraisal skills to promote emotion regulation and restructure motivations for highly palatable food intake; and savoring pleasant events and emotions to overcome defects in natural reward processing. In addition to class sessions, participants will complete daily, 15-minute, audio-guided mindfulness, reappraisal, and savoring sessions at home. The intervention will be delivered by a study team member who will receive training and supervision from [name]. Treatment fidelity will be monitored as in ongoing RCTs of MORE (E. L. Garland, Manusov, et al., 2014).
- **CON:** Participants randomized to the control intervention will complete an 8-week healthful lifestyle program via HIPPA compliant zoom sessions. The curriculum will be based on the Diabetes Prevention Program's Prevent T2 for Life program, which is an evidence-based national healthful lifestyle maintenance intervention. This program includes training in healthful eating, meal planning, and recipe modification; time and stress management; adapting lifestyle habits for continued success during holidays, vacations, and other special situations; and relapse prevention. CON will be virtually delivered by a study team member who will receive training and oversight from [name], who has delivered this intervention previously. In addition to class sessions, participants will be completed daily, 15-minute activities related to the course content (i.e. – designing a meal plan and grocery shopping list; creating a list of healthful take-out or restaurant meals; etc) at home. Time-in-treatment will be matched between conditions.

POST-INTERVENTION TESTING: Repeat baseline testing at the end of 8 weeks and at 6 months.

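### Weight-loss route is neither a stratum nor a named covariate in the body-mass model, and a route main effect alone would leave the intervention-by-time contrast unadjusted (low-priority improvement)

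*Combined protocol and SAP*

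**What the plan says.** The inclusion criteria (Study Population) open with "We will enroll the following three subgroups (ages 18-65 years" and then list lifestyle, medical and bariatric-surgery participants. The first two share one window: a 7% intentional loss in the past 6 months, with 3 months of stable medication added for the medical group. Surgery participants enter 12-20 months after the operation and are excluded if they have regained more than 5%. No target share per route is given.

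Under Randomization, "block randomization will be performed within strata defined by sex". Route is not a stratum.

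Under Statistical Methods, Aim 1 concerns the "primary outcome of body mass and body composition at week 8 and week 24". The mixed model is to be fitted "controlling for covariates likely to be associated with the outcome". The named covariates are baseline body mass and composition, and "other demographic covariates including (but not be limited to) age, sex, race and socioeconomic status". On time, the plan says "Different slopes for time trend and intervention-time interaction term will be assumed" for the two periods. On correlation, it says "Random intercepts will be used to account for correlations on the participant level". The sample-size section concedes limited power, adds "We expect power will be greater for our primary analysis models when adjusting for covariates associated with outcomes", and says the trial is to supply an effect size for a future one.

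Route appears in no stratum, named covariate, interaction or subgroup analysis.

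**The concern.** The outcome is weight regain, and the protocol defines its subgroups by how and when weight was lost. Someone more than a year past surgery may well be on a different weight course from someone within six months of a 7% loss, whichever arm they are in. If so, a chance excess of one route in one arm shows up as a difference in slope between arms.

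The open covariate rule looks like a sufficient answer, but the form of the covariate matters. A covariate that is constant over time and entered as a main effect shifts a participant's whole curve up or down. It cannot change slopes, and the intervention effect is expressed through slopes. An analyst could follow the plan, add route in the usual way, and leave the intervention-by-time contrast as exposed as before. At stake is the stability of the estimate meant to size the next trial.

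**Working it through.** The plan has no figure of its own on this point, so there is none to reproduce. Everything below rests on stated assumptions.

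**Inputs from the documents.** 100 participants, 1:1, 20% attrition, weekly body mass in weeks 0-24, slopes changing at week 8, random intercept, baseline mass as covariate.

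**Assumed.** Equal thirds per route; one route differs from the other two by d kg at week 24; SD of 24-week change S = 3 or 5 kg; share of its variance explained by route R² = 5%, 10% or 20%. The only variability figure in the documents is the pilot result in the introduction (±1.2% of body weight around an 8-week programme, n=7). If that is an SD, body weight is 80-100 kg and spread grows linearly, it gives 0.012 × 80 × 3 = 2.9 kg to 0.012 × 100 × 3 = 3.6 kg at 24 weeks.

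**1. How likely is an imbalance?** Take a gap of at least 10 points in one route's share, with 50 per arm. The hypergeometric probability is 0.395 if 33 of 100 belong to the route and 0.291 if 34 do. The two differ because the count difference must be odd or even. It is 0.262 if 15 of 100 do.

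**2. Shift without route terms.** With share p, d = S × √(R² / [p(1-p)]), and a 10-point gap shifts the week-24 estimate by 0.1 × d. For p = 1/3, p(1-p) = 0.222.

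| R² | S = 5 kg: d, shift | S = 3 kg: d, shift |
|---|---|---|
| 5% | 2.37, 0.24 kg | 1.42, 0.14 kg |
| 10% | 3.35, 0.34 kg | 2.01, 0.20 kg |
| 20% | 4.74, 0.47 kg | 2.85, 0.28 kg |

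Simulation at S = 5 kg (8,000 trials per setting, no true arm effect, 20% random dropout, routes diverging linearly) gave 0.229, 0.352 and 0.480 kg, or 0.21, 0.33 and 0.45 of the estimate's empirical SD. Multiplied by 3/5, these are about 0.14, 0.21 and 0.29 kg.

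**3. What a route main effect does.**

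*Intervention-by-time contrast* (8 × first-period interaction + 16 × second-period interaction). With complete data, slopes in a random-intercept model are estimated within participants, so a time-constant covariate cannot alter them. The simulated change was 0.00000 kg in every complete-data run, weekly or at weeks 0/8/24. With weekly data and dropout, in the linear setting, no single estimate moved by more than 0.045 kg, and the shifts stayed at 0.229, 0.352 and 0.480 kg.

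*Baseline-adjusted arm difference.* With complete data the route coefficient settles at the time-average of the route difference. The fraction of the week-24 shift removed is therefore that average divided by the week-24 value. For the 25 weekly weights:

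- Linear divergence: 12/24 = 50%
- Early (weeks 0-8, then flat): (4.5 + 16)/25 = 82%
- Late (weeks 8-24 only): 8.5/25 = 34%

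At weeks 0/8/24 the fractions are 44%, 67% and 33%. With weekly data and dropout, simulation gave 42-46% for linear (for example 0.356 to 0.205 kg at R² 10%), about 72% for early and about 28% for late.

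At week 8 the same constant is subtracted from a shift that, as a fraction of its week-24 value, is 0.33 (linear), 1.00 (early) or 0 (late). That leaves 0.33 - 0.50 = -0.17, 1.00 - 0.82 = +0.18 and 0 - 0.34 = -0.34. So there is over-correction with linear or late divergence, and none with early.

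**4. What route-by-period terms do.** The remaining shift was at most 0.022 kg on either contrast (linear setting). Empirical SD in kg at week 24, S = 5 kg, equal thirds:

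| R² | Interaction contrast: none / main / by period | Baseline-adjusted: none / main / by period |
|---|---|---|
| 0 | 1.074 / 1.073 / 1.086 | 1.085 / 1.087 / 1.097 |
| 5% | 1.072 / 1.072 / 1.060 | 1.087 / 1.074 / 1.075 |
| 10% | 1.074 / 1.074 / 1.028 | 1.083 / 1.051 / 1.038 |
| 20% | 1.078 / 1.077 / 0.977 | 1.092 / 1.024 / 0.992 |

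On the interaction contrast, by-period terms change the SD by +1% (1.086/1.074), -1%, -4% and -9% (0.977/1.078). On the baseline-adjusted contrast a main effect alone already gives -1%, -3% and -6% for R² 5%, 10% and 20%.

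**The case against.** The strongest reply is that the plan already commits to adjusting for covariates associated with the outcome and leaves the list open, so route is covered if it matters. Part of this stands: the plan does not exclude route, and a reader who infers that it does goes too far. What is missing is the form, and the usual form does not reach the intervention-by-time contrast.

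Second, the gain is small. At R² of 5-10% it is 1-4% in SD, and on the baseline-adjusted contrast a main effect already captures most of it. This stands, and it sets the priority.

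Third, no passage shows that weight course differs by route, and lifestyle and medical participants share the same 6-month window. This also stands. The documents support a timing contrast mainly between surgery and the other two routes, and the 5% regain limit may narrow even that.

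Fourth, one might infer that a main effect always removes just under half of the shift and over-corrects at week 8. That holds only for linear divergence with dropout, and the documents give no trajectories.

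Finally, the random-intercept-only structure is a larger problem. In the simulations the model SE on the interaction contrast was about 0.25-0.27 kg against an empirical SD of 0.98-1.09 kg, and nominal 5% tests rejected in 62-64% of null trials with or without route terms. That is true, but it is a separate matter.

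**Conclusion.** The point holds as an optional, low-priority improvement. Route is not pre-specified, and adding it as a main effect would leave the intervention-by-time contrast essentially unadjusted and the baseline-adjusted week-24 difference only partly adjusted (roughly 30% to 80%, by timing of divergence). The conclusion about the main effect does not depend on whether weights are weekly, as in the analysis section, or taken at baseline, 8 weeks and 6 months, as in the procedures.

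The sizes in kg are illustrative. They depend on assumed route shares, an assumed R² of 5-20% and an assumed change SD of 3-5 kg. If route explains nothing, there is nothing to gain.

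Two stronger readings are not supported. One is that omitting route biases the trial: randomisation keeps the estimate unbiased on average, and what remains is imbalance in the realised sample and some loss of precision. The other is that route terms would make the planned test valid: they do not cure the understated standard errors.

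**What to change.** Before the arms are compared, add to the Aim 1 model description that route (three levels) and its interaction with both period slopes (weeks 0-8 and 8-24) enter the primary body-mass model. Also report route by arm in the baseline table. Surgery versus the other two routes is an acceptable smaller form.

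The cost is SAP wording and a table row; route is already established for eligibility, so no new data or participants are needed. The three-level form uses up to six degrees of freedom (two for route, four for its time interactions); the two-level form uses three (one plus two). If route explains nothing, the empirical SD rises by about 1-2%.

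Stratifying randomisation by route would help only if allocation were still open. The consent section says enrolment will be over as of March 2023, so adjustment in the analysis is probably the remaining route. Similar terms for Aim 2 outcomes are optional and were not assessed here.

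### Single-step Bonferroni is valid, but Holm's step-down procedure gives the same error control and never rejects fewer hypotheses: an optional, nearly free improvement

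*Combined protocol and SAP*

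**What the plan says.** The first paragraph under Statistical Methods, Data Analysis and Interpretation ends: "Bonferroni correction will be performed to adjust for multiple comparisons". That is the whole multiplicity plan. It does not list the comparisons, count them, state alpha or sidedness, or say why the single-step method was chosen. No simultaneous confidence intervals are planned.

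The sentence follows the description of both aims. Aim 1 concerns "the primary outcome of body mass and body composition at week 8 and week 24". For the second aim, "LMM will be fitted for each of the eating behaviors and energy intake outcome collected for" Aim 2. The Baseline Testing list gives about nine such measures: restraint, disinhibition, hunger, self-efficacy, cravings, interoceptive awareness, savoring, free-living intake and ad libitum intake. Testing is repeated at 8 weeks and 6 months.

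The sample size paragraph reads "For a total of 100 participants randomized 1:1 to each study arm, we conservatively anticipate 20% attrition", which leaves 40 per group. It claims at least 80% "power for detecting differences in body mass (or other outcomes assessed in Aim 1 and 2) by at least 0.89 standard deviations" and concedes that "we will have limited statistical power for the current analysis".

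**The concern.** Bonferroni compares every p-value with alpha/m, where m is the number of tests, however many effects have already been established. Holm starts at the same alpha/m but relaxes the threshold after each rejection, with no added assumption. A plan that tests many outcomes and describes its own power as limited could therefore keep some power that it now gives up.

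Aim 2 is the natural place for this to matter. Its hypothesis is that eating behaviors and energy intake change together, both after the intervention and at 6 months. Holm helps when several effects in one family are real. What is at stake is the second and later findings in a family, not whether the trial finds anything.

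**Working it through.** **Inputs.** From the sample size paragraph: 100 randomized, 1:1, 20% attrition, 0.89 SD, power of at least 80%. Assumed, because the documents do not give them: two-sided family-wise alpha 0.05, m from 4 to 20, and equal correlation of 0.3 to 0.6 between tests.

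**The plan's own figure.** 100 × 0.8 = 80, or 40 per arm. For a standardized difference d, the test statistic is centred on d × √(40/2) = d × √20. At 0.89 SD this is 3.980. At unadjusted two-sided 0.05, power is Φ(3.980 − 1.960) = 97.8% (97.6% with the t distribution), and the effect detectable with 80% power is (1.960 + 0.842)/√20 = 0.63 SD. So 0.89 SD is not the 80% detectable effect at unadjusted 0.05 with 40 per arm, although a claim of at least 80% is literally true. A t-test at 0.05/20 = 0.0025 gives 79.95%. So, nearly, does 20 per arm at unadjusted 0.05: 2.802 × √(2/20) = 0.886 SD. The documents do not say which was used, so the family size cannot be recovered from this figure.

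**Error control.** Order the p-values. Holm compares the j-th smallest with 0.05/(m − j + 1) and stops at the first failure. For m = 8 the thresholds are 0.00625, 0.00714, 0.00833, 0.01, 0.0125, 0.01667, 0.025 and 0.05; Bonferroni uses 0.00625 throughout. Let m₀ hypotheses be truly null. When the first of them is rejected, at most m − m₀ others have gone before, so its threshold is at most 0.05/m₀. The chance that any of m₀ null p-values falls below 0.05/m₀ is at most 0.05, whatever the dependence.

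**Dominance.** A p-value at or below 0.05/m passes every Holm threshold, and so does every smaller one. Every Bonferroni rejection is therefore a Holm rejection. The first thresholds are equal, so the chance of at least one rejection is identical.

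**Size of the gain.** Bonferroni power per test is Φ(d√20 − z), with z the critical value at 0.05/m. For m = 8 and d = 0.6: Φ(2.683 − 2.734) = 48%. For m = 20 and d = 0.7: Φ(3.130 − 3.023) = 54%. For m = 20 and d = 0.89: Φ(3.980 − 3.023) = 83%. Holm power comes from simulated equicorrelated z-statistics (20,000 replicates, correlation 0.3 and 0.6), averaged over the true effects:

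| Tests | Real effects | Size (SD) | Bonferroni | Holm | Gain (points) |
|---|---|---|---|---|---|
| 8 | 1 | 0.6 | 48% | 48% | 0 |
| 8 | 2 | 0.6 | 48% | 49% | about 1 |
| 8 | 4 | 0.6 | 48% | 51% | about 3 |
| 8 | 8 | 0.3 | 8% | 9–10% | 1–2 |
| 4 | 4 | 0.6 | 57–58% | 66–67% | about 9 |
| 8 | 8 | 0.6 | 48% | 58% | about 10 |
| 20 | 20 | 0.7 | 54% | 66–67% | 12–13 |
| 20 | 20 | 0.89 | 83% | 92–94% | 9–11 |

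With 20 tests, ten of them real at 0.89 SD, t-based simulation at correlation 0 and 0.5 gives 80% against 83–84%, a gain of 3–4 points. Gains are also small where power is already near its ceiling: with two tests, both real at 0.89 SD, 95% becomes 97%. No Bonferroni rejection was lost, and Holm's simulated family-wise error at these correlations was at most 0.045.

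**The case against.** The strongest case against is that nothing here is wrong. Bonferroni is prespecified and controls the error rate, and no estimate or conclusion becomes invalid. That stands: the point is about efficiency only.

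Several stronger readings are tempting, and the documents do not support them:

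- *That a gain of around 10 points should be expected.* This needs every test in the family to be a real and large effect. The plan hypothesises joint change but gives no data for it, and says that the effect size is still to be learned.
- *That real effects are missed only because of the adjustment method.* With eight real effects of 0.6 SD, Holm still misses 100 − 58 = 42% of them, against 100 − 48 = 52%. Most misses come from the sample size and from correcting at all.
- *That Holm cures the limited power the plan concedes.* The first threshold is the same, so the chance of any finding is unchanged.
- *That the sentence certainly covers every comparison in the trial.* It is unqualified, but it follows the Aim 2 text and could be read as Aim 2 only.

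Two further objections stand in part. Bonferroni has simple matching simultaneous intervals, and a trial meant to inform a later one will care about intervals; however, the plan asks for no simultaneous ones. Also, the plan lists no family, number of tests or alpha. Neither method can be carried out until it does, and that is the larger gap. It does not favour Bonferroni, since Holm is no worse for whatever family is declared.

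**Conclusion.** The point holds as an optional improvement. For hypothesis testing, single-step Bonferroni is dominated by Holm: same family-wise control under any dependence, and never fewer rejections. That comparison is mathematical and does not depend on the assumptions.

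The size does depend on them (two-sided 0.05, 4 to 20 tests, correlation 0.3 to 0.6, 40 per arm). The gain in average power per true effect is 0 with one real effect, about 1 point with two of eight, and about 3 to 4 points with half real. It reaches about 9 to 13 points only when all are real at 0.6 to 0.89 SD. If all eight are real but only 0.3 SD, it is 1 to 2 points. Effect estimates are untouched. The documents do not allow one figure to be chosen from this range.

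**What to change.** Replace the multiplicity sentence with:

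*Within each declared family of tests, the Holm step-down procedure will control the family-wise error rate at two-sided 0.05; Holm-adjusted p-values will be reported with unadjusted 95% CIs, labelled as unadjusted and not used for the significance decision.*

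The labelling matters because an unadjusted interval can exclude zero while the adjusted p-value exceeds 0.05. If simultaneous intervals are wanted, Bonferroni intervals can be added. The families themselves must be listed for this sentence to work, as they must for Bonferroni.

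The cost is one sentence and one software option, with no change to sample size, data collection or conduct. The change should be made before comparative results are seen, because a later switch would look data-driven.
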